Document:

Study protocol and statistical analysis plan

Protocol:

EFFECT OF A NUTRITIONAL SUPPORT SYSTEM (DIET, SUPPLEMENTS AND PROBIOTIC) FOR IMPROVING GROSS MOTOR FUNCTION IN CEREBRAL PALSY. AN EXPLORATORY RANDOMIZED CONTROLLED CLINICAL TRIAL

NCT number:

2014/03001

Date:

March 28, 2014

EFFECT OF A NUTRITIONAL SUPPORT SYSTEM (DIET, SUPPLEMENTS AND PROBIOTIC) FOR IMPROVING GROSS MOTOR FUNCTION IN CEREBRAL PALSY. AN EXPLORATORY RANDOMIZED CONTROLLED CLINICAL TRIAL

Abstract

Background: Most patients with cerebral palsy (CP) are dependent on parents due to the spasticity and limitations in their gross motor function. Additionally, many of them do not respond to physical therapy due to deterioration in their nutritional status, which is secondary to gastrointestinal disorders, parasitosis, dysbiosis and the catabolic state of the disease itself. Evidence suggests that greater independence and better clinical response can be achieved by correcting the nutritional status. However, basic treatments only contemplate the calculation of energy requirements and do not consider important nutrients in particular, supplementation with glutamine, arginine, zinc, selenium, colexicaliferol, nicotinic acid, spirulina, omega 3, ascorbic acid, vegetal protein or even probiotics.

Objective: To determine the effect of using a nutritional support system (NSS) diet, supplements and probiotic on the gross motor function in children with CP with spastic diparesic and Gross Motor Function Classification System III (GMFCS III).

Material and methods: In an exploratory study with controlled clinical trial design, 30 patients were randomly assigned to receive: 1) dietary surveillance and conventional therapy (FG), 2) deworming and WHO diet (CG), or 3) deworming and the NSS (IG). The patients were recruited from the CRIT Tlalnepantla Estado de México. Males and females aged 4-12 years were included with CP and spastic diparesic GMFCS III, and who had a full-time caregiver and whose parents agreed to participate. They were studied for thirteen weeks. Gross motor function was evaluated at baseline and at 7 and 13 weeks after therapy using the GMFM scale.

Results: The IG-treated group presented a significant improvement in standing and walking parameters analyzed in the GMFM compared with FG and CG groups. Fifty percent of the IG-treated patients managed to walk, while in the other groups no patients were able to walk.

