2.6 GMFM assessment

The GMFM scale was performed at baseline time and weeks 7 and 13 after intervention. It was applied by CRIT staff. The evaluators were the blind aspect of the study as they did not have access to any information about the treatment each child was receiving.

This scale assesses five general parameters: 1. Lying (decubitus) and rolling over (GMFAV), 2. Sitting (GMFB), 3. Crawling and kneeling (GMFC), 4. Standing (GMFD), 5. Walking (GMFE) and one final total item (GMFF). The scoring system consists of 88 items and each one is valued based on the following criteria: 0= No, 1= start, 2= Partially Complete, 3= Complete, NE= Not evaluated [18-19].

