2.7 Statistical methods

In order to know the type of distribution of the data, the tests of Kolmogorov-Smirnov, D'Agostino-Pearson and Shapiro-Wilk were applied. Analysis of data was performed using

the continuous variables mean and standard deviation were used if the distribution was normal, and if it didn't present normal distribution the median and range were used. Percentages and proportions assessed the ordinal variables. Analysis of data with normal distributions was performed using One-way ANOVA. ANOVA of repeated measurements was used to analyze the intragroup difference. When the distribution did not show normality, Kruskal Wallis test followed by the Dunn post hoc test. and Tukey were applied respectively to post hoc tests. The level of significance was <0.05 in all cases.

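### With six GMFM scores, two follow-up visits, no named primary and every test read at 0.05, this exploratory trial supports a hypothesis, not its unqualified conclusion of benefit

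*Combined protocol and SAP*

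**What the plan says.** - **Objective (Abstract):** "To determine the effect of using a nutritional support system (NSS) diet, supplements and probiotic on the gross motor function in children with CP". No score or visit is specified.
- **Outcome (section 2.6):** "This scale assesses five general parameters" (lying and rolling, sitting, crawling and kneeling, standing, walking), and a total is added, which makes six scores. On timing: "The GMFM scale was performed at baseline time and weeks 7 and 13 after intervention".
- **Analysis (section 2.7):** one-way ANOVA between arms for normal data. Otherwise: "When the distribution did not show normality, Kruskal Wallis test followed by the Dunn post hoc test". Tukey is also listed as a post hoc test. Repeated-measures ANOVA is used for change within an arm. The threshold is: "The level of significance was <0.05 in all cases". For categorical data the section says only: "Percentages and proportions assessed the ordinal variables".
- **Status:** the title, the Abstract and section 2 all call the study exploratory.
- **Results (Abstract):** the intervention group (IG) "presented a significant improvement in standing and walking parameters analyzed in the GMFM compared with FG and CG groups", meaning the follow-up group (FG) and the conventional group (CG). Also: "Fifty percent of the IG-treated patients managed to walk, while in the other groups no patients were able to walk".
- **Conclusion (Abstract):** a flat statement that the system improves gross motor function and brings about walking, with no mention of the exploratory design.

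**The concern.** The exploratory label and the conclusion do not match. Unadjusted testing of several scores is tolerable when the output is offered as a hypothesis. Here the plan uses the freedom of an exploratory study, and the conclusion then reads like that of a confirmatory one.

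Dunn and Tukey deal with pairs of arms inside one analysis. Repeated-measures ANOVA deals with visits, but only within an arm. Nothing described deals with the six scores, or with between-arm tests repeated at weeks 7 and 13. A reader told that two scores were significant cannot see how many comparisons lie behind them, or what the other four scores showed.

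The walking half of the conclusion may rest on the proportion who walked. Sections 2.6 and 2.7 as supplied neither define that proportion as an outcome nor name a between-arm test for it. What is at stake is how much weight the conclusion can carry.

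**Working it through.** The documents state no overall error rate, power or sample-size calculation, so there is no figure to reproduce.

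**Inputs from the documents.** Three arms of 10 (section 2.2); six scores and two post-baseline visits (section 2.6); ANOVA with Tukey, each test at 0.05 (section 2.7).

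**Assumptions.** All six scores are tested between arms at both visits: 6 × 2 = 12 tests. There is no true effect, the data are normal, and the total is the mean of the five dimensions. Correlation is 0.3–0.7 between scores and 0.8–0.9 between visits.

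**Step 1: independent tests, as an upper reference.** Chance of at least one false positive = 1 − 0.95^m.
- m = 6: 1 − 0.95^6 = 26.5%.
- m = 12: 1 − 0.95^12 = 46.0%.

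**Step 2: correlated scores, by simulation.** A test counts if F exceeds 3.354 (2 and 27 df). IG beats both arms if its mean exceeds each of the others by more than 3.506 × √(MSE/10), the Tukey limit.

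| Event under no effect | One test | Week 13, six scores | All 12 tests |
|---|---|---|---|
| Any group difference, any direction | 5% | 16–22% | 21–33% |
| IG better than both arms on at least one test | 0.15% | not tabulated | 1.0–1.5% |
| IG better than both arms on at least two dimensions at the same visit | – | – | 0.03–0.23% |

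**Step 3: sensitivity.** Section 2.1 describes these children as already functioning well in lying and rolling, sitting and crawling. Placing 30% or 60% of children at ceiling on those three dimensions, with Kruskal-Wallis used for them, gives 22–34% over 12 tests and 16–22% at week 13. Taken with Step 2, the 12-test range is 21–34%. If all scores and visits shared one common correlation of 0.9, the figures would fall to 14.7% for 12 tests and 11.6% for six, still above 5%.

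**Step 4: walking.** Assume all 10 per arm were analysed, so 5/10, 0/10 and 0/10.
- Pairwise Fisher, two-sided: 2 × C(10,5)/C(20,5) = 504/15,504 = 0.033 against each comparator.
- Three-arm exact test: 3 × C(10,5)/C(30,5) = 756/142,506 = 0.005.
- Closed testing (three-arm test first, then pairs): adjusted pairwise p = max(0.005, 0.033) = 0.033.
- Holm over the two comparators: 2 × 0.0325 = 0.065.
- Exact 95% intervals: 19–81% for IG. For each other arm the upper limit is 1 − 0.025^(1/10) = 31%, giving 0–31%.

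The pairwise walking result falls on either side of 0.05 depending on a procedure that the supplied text does not name.

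**The case against.** The case for leaving the plan alone is substantial.

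- **An exploratory study need not control familywise error, and the plan does not claim to.** This stands. The 0.05 sentence is not an error in itself.
- **The 21–34% counts differences nobody claims, such as FG against CG.** This stands. A reader might infer from that range that the standing and walking findings are products of multiple testing. The documents do not support this: the claim is that IG beat both arms, and chance yields that on even one of 12 tests only about 1.0–1.5% of the time.
- **Standing and walking are not arbitrary choices.** Section 2.1 enrols children already strong on the other three dimensions and excludes those who walk by themselves, so most room for change lies in these two. This weakens any suspicion of selective reporting, but it does not amount to naming a primary.
- **Visits are covered by repeated-measures ANOVA.** This is true within an arm. It does not cover between-arm tests at the two visits.
- **The walking evidence is stronger than a Holm-adjusted 0.065 suggests.** This is fair. Closed testing keeps 0.033 and follows the omnibus-then-pairs order of section 2.7.
- **Text may be missing.** One sentence in section 2.7 breaks off in the supplied text, and the flow diagram is not shown. A named test for proportions may have been lost, and the analysed numbers are unknown. The threshold sentence is intact, however, and neither the objective nor section 2.6 names a primary.

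None of this justifies a conclusion without qualification.

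**Conclusion.** The point holds as a mismatch between design and conclusion. Six scores, two follow-up visits, no named primary and unadjusted tests at 0.05 can generate a hypothesis; they cannot establish an effect. Under the stated assumptions, the chance of some false group difference is about 21–34% over 12 tests, or 16–22% if only week 13 was tested, against 5% for a single test. The specific pattern reported is much harder to obtain by chance, so this is not evidence that the result is wrong.

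The size depends on three things the documents do not give: which scores and visits were compared between arms (and whether as change scores), the correlations, and the numbers analysed for walking. The mismatch itself depends on none of them. This is a cheap improvement that changes what the trial may conclude, not a flaw that invalidates it.

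**What to change.** 1. Reword the Abstract's Conclusion as hypothesis-generating, unless a dated document from before the data were seen names a primary score and visit and that comparison is positive. Without such a document, do not name a primary now.
2. Report between-arm estimates with 95% confidence intervals for all five dimensions and the total at weeks 7 and 13, not only standing and walking. State how many between-arm tests were run.
3. Report walking as counts with exact 95% intervals, name the test and any adjustment used, and say whether it was planned.

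Holm across the six scores is optional and should not be required. The scores overlap, an adjustment chosen after the data were seen would not make the results confirmatory, and the power cost is large. For an assumed effect of 1.5 SD on standing and walking, the chance that IG beats both arms on standing at week 13 would fall from about 70% to about 41%.

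The cost is a softer conclusion and a little more reporting from existing data. No new data are needed.
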